- (3) Dead/diminished areas – establish a baseline amplitude for sensation and leave signal on at this amplitude. Over time assess if the amplitude for sensation is decreased demo return of sensation.
- (4) Hot spots – assess if the same amplitude over these areas which creates high level of discomfort becomes less uncomfortable over time as a sign of increased neurological resiliency.
- iv) Continue with electrodes in place and apply with functional training in high kneeling, sitting, transfers, standing static, standing dynamic closed chain, standing dynamic open chain, gait and movements available in LE/core
- v) Progress participant in sitting balance unsupported, sit to stand, standing balance static and dynamic and in gait
- vi) If participant tolerates less amplitude signal next visit while working through spasticity or contraction, they are in neurological fatigue and consider master re-set, sensory inputs, stretches and more gentle approach for active recovery

If participant was not receiving this intervention, they would receive traditional physical therapy in stretching, therapeutic exercise training open chain and closed chain, transfer training, gait training and balance training working within limits of participant's spasticity levels.

Participants in this study will participate in the listed interventions for 6 weeks. Outcome measures objective and subjective will be collected at the beginning and end of the study.

1. EDSS – [name] performs (<https://www.mstrust.org.uk/a-z/expanded-disability-status-scale-edss>)
2. Hoffman's Reflex – [name] performs ([name] performs test only, then gives results to investigators.) (<https://www.ncbi.nlm.nih.gov/pmc/articles/PMC522151/>)
3. 12 item MS walking scale –[name] performs <https://www.sralab.org/sites/default/files/2017-07/msws-eng.pdf>
4. Manual Muscle test – [name] performs
5. Modified Ashworth test – [name] performs <https://www.sralab.org/sites/default/files/2017-06/Modified%20Ashworth%20Scale%20Instructions.pdf>
6. 25 foot walk test – [name] performs [https://www.nationalmssociety.org/For-Professionals/Researchers/Resources-for-Researchers/Clinical-Study-Measures/Timed-25-Foot-Walk-\(T25-FW\)](https://www.nationalmssociety.org/For-Professionals/Researchers/Resources-for-Researchers/Clinical-Study-Measures/Timed-25-Foot-Walk-(T25-FW))
7. Timed up and Go –[name] performs https://www.cdc.gov/steadi/pdf/TUG_test-print.pdf

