Date: July 21, 2022

Data: sent to [name] via email by PT [name]

Goal: Evaluate 7 patients with MS on functional scale prior, during, and post participation in a rehab program

Note: 7 patients is a very low sample size to have any kind of confidence in our results, especially since this is a heterogeneous group of patients with varying disease severity. These results should be considered a pilot and interpreted with caution.

Analyses:

A within subjects repeated measures ANOVA with no between subject factor was used to assess for linear and quadratic (for variables measured at all 3 time points) trends for continuous variables.

Continuous variables were: quad length, 25 foot walk test, HS length, TUG test, HIP IR ROM, HIP ER ROM. Results from these analyses are shown on page 2 (top portion of table).

Paired samples t-tests were used to assess for mean change over time for continuous variable measured at 2 timepoints (pre and post). SPSS version 28.0 was used for analyses. Results from these analyses are shown on page 2 (bottom portion of table).

The MAT and MMT measures were analyzed descriptively (no p-values). Counts and percentages are reported in table on page 3.

Summary of Statistically Significant Findings:

1. A linear trend emerged for HIP IR ROM for both the right and the left side. With ROM increasing over time.
 - a. Right side means: 6.9, 12.1, 15.3; P=.003
 - b. Left side means: 10.7, 13.4, 17.9; P=.016

Table of means over time for tests that are considered continuous measures. Variables highlighted in yellow are statistically significant. In both cases hip internal rotation increased in a significant linear fashion throughout the 3 time points.

The tests below were administered at all three time points. A repeated measures model with time as the within subjects variable and no between subjects variable was used to assess for linear and quadratic trends. There were no quadratic trends reported. There were 2 significant linear trends reported, Hip IR ROM left and right side

| Test | Mean (Std Error), pre | Mean (Std Error), during | Mean (Std Error), post | P-value |
|--------------------|-----------------------|--------------------------|------------------------|---------|
| Quad Length R | 122.5 (5.9) | 130.8 (1.6) | 130.0 (2.6) | 0.312 |
| Quad Length L | 121.7 (5.6) | 130.0 (1.3) | 130.8 (2.4) | 0.210 |
| 25 foot walk test | 21.4 (5.2) | 20.7 (5.9) | 15.0 (1.3) | 0.370 |

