| Hamstring length R | 67.5 (4.4) | 52.5 (18.7) | 55.0(15.6) | 0.470 |
| Hamstring length L | 64.0 (7.8) | 72.0 (4.6) | 74.0 (3.7) | 0.189 |
| TUG Test | 27.2 (9.2) | 23.6 (6.9) | 16.5 (0.4) | 0.321 |
| Hip IR ROM R | 6.8 (1.8) | 12.1 (2.1) | 15.3 (2.1) | 0.003 |
| Hip IR ROM L | 10.7 (2.3) | 13.4 (1.3) | 17.9 (1.5) | 0.016 |
| Hip ER ROM R | 34.3 (6.3) | 38.6 (5.5) | 38.3 (6.0) | 0.199 |
| Hip ER ROM L | 35.0 (5.8) | 38.6 (5.0) | 40.0 (5.7) | 0.134 |

The data below were collected at 2 timepoints. Means from pre to post were compared using a paired samples t-test. Means \pm standard deviations are reported. P -values are not significant.

| Test | Mean \pm SD, pre | | Mean \pm SD, post | p-value |
|--------|--------------------|----|---------------------|---------|
| EDSS | 6.8 \pm 0.8 | -- | 6.8 \pm 0.8 | NA |
| MSIS29 | 97.3 \pm 25.2 | -- | 85.0 \pm 20.2 | 0.397 |
| MSWS12 | 0.89 \pm 0.14 | -- | 0.70 \pm 0.28 | 0.277 |

On the following page assessments for categorical measures are shown by the count and percentage of patients who improved, stayed the same, and worsened over time (from pre to post).

| | N worse | N same | N Improve | %worse | %same | %Improved |
|--|---------|--------|-----------|--------|--------|-----------|
| MATR hip fleX change | 0 | 5 | 2 | 0.0% | 71.4% | 28.6% |
| MATL hip flex change | 0 | 6 | 1 | 0.0% | 85.7% | 14.3% |
| MATR hip ext change | 1 | 2 | 4 | 14.3% | 28.6% | 57.1% |
| MATL hip ext change | 2 | 4 | 1 | 28.6% | 57.1% | 14.3% |
| MATR knee flex change | 1 | 4 | 2 | 14.3% | 57.1% | 28.6% |
| MATL knee flex change | 0 | 3 | 4 | 0.0% | 42.9% | 57.1% |
| MAT R knee ext change | 1 | 5 | 1 | 14.3% | 71.4% | 14.3% |
| MAT L knee ext change | 0 | 3 | 4 | 0.0% | 42.9% | 57.1% |
| MAT R ankle DF change | 1 | 6 | 0 | 14.3% | 85.7% | 0.0% |
| MAT L ankle DF change | 0 | 7 | 0 | 0.0% | 100.0% | 0.0% |
| MAT R Ankle PF change | 1 | 1 | 5 | 14.3% | 14.3% | 71.4% |
| MATL ankle PF change | 2 | 0 | 5 | 28.6% | 0.0% | 71.4% |
| MMT R psoas Change | 0 | 3 | 4 | 0.0% | 42.9% | 57.1% |
| MMT L psoas Change | 0 | 2 | 5 | 0.0% | 28.6% | 71.4% |
| MMT Rec Abd change | 0 | 3 | 3 | 0.0% | 50.0% | 50.0% |
| MMT R Quadratus Change | 0 | 2 | 5 | 0.0% | 28.6% | 71.4% |
| MMT L Quadratus Change | 0 | 3 | 4 | 0.0% | 42.9% | 57.1% |
| MMT R Rec Fem Change | 1 | 2 | 4 | 14.3% | 28.6% | 57.1% |
| MMT L Rec Fem Change | 1 | 3 | 3 | 14.3% | 42.9% | 42.9% |
| Vastus R lateralis medialis MMT Change | 1 | 1 | 5 | 14.3% | 14.3% | 71.4% |

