| Vastus L lateralis medialis MMT Change | 0 | 0 | 7 | 0.0% | 0.0% | 100.0% |
| MMT R Glut Med Change | 0 | 0 | 7 | 0.0% | 0.0% | 100.0% |
| MMT L Glut med Change | 0 | 3 | 4 | 0.0% | 42.9% | 57.1% |
| MMT R Hip Add Change | 1 | 1 | 5 | 14.3% | 14.3% | 71.4% |
| MMT L Hip Add Change | 0 | 2 | 5 | 0.0% | 28.6% | 71.4% |
| MMT R Fibularii Change | 3 | 2 | 2 | 42.9% | 28.6% | 28.6% |
| MMT L Fibularii Change | 2 | 3 | 2 | 28.6% | 42.9% | 28.6% |
| MMT R Tib anterior CHANGE | 0 | 2 | 5 | 0.0% | 28.6% | 71.4% |
| MMT L Tib anterior Change | 1 | 1 | 5 | 14.3% | 14.3% | 71.4% |
| MMT R Tib posterior Change | 3 | 2 | 2 | 42.9% | 28.6% | 28.6% |
| MMT L Tib posterior Change | 2 | 3 | 2 | 28.6% | 42.9% | 28.6% |
| MMT R toe Ext Change | 1 | 2 | 4 | 14.3% | 28.6% | 57.1% |
| MMT L toe Ext Change | 2 | 3 | 2 | 28.6% | 42.9% | 28.6% |
| MMT R toe flex Change | 2 | 2 | 3 | 28.6% | 28.6% | 42.9% |
| MMT L toe flex Change | 1 | 4 | 2 | 14.3% | 57.1% | 28.6% |
| MMT lumbar ext B | 1 | 0 | 4 | 20.0% | 0.0% | 80.0% |
| MMT R glut max Change | 0 | 3 | 4 | 0.0% | 42.9% | 57.1% |
| MMT L glut max Change | 2 | 2 | 3 | 28.6% | 28.6% | 42.9% |
| MMT R biceps Fem Change | 0 | 2 | 4 | 0.0% | 33.3% | 66.7% |
| MMT L biceps Fem Change | 0 | 1 | 5 | 0.0% | 16.7% | 83.3% |
| MMT R semitendinosis semimembranosis | 0 | 2 | 5 | 0.0% | 28.6% | 71.4% |
| MMT L semitendinosis semimembranosis | 1 | 4 | 2 | 14.3% | 57.1% | 28.6% |

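### The printed MSWS-12 paired t-test cannot plausibly come from 7 complete pairs, and neither questionnaire row says how many pairs were tested

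*SAP*

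**What the plan says.** The SAP opens with its purpose: "Goal: Evaluate 7 patients with MS on functional scale prior, during, and post participation in a rehab program". The protocol (Procedures Involved) sets the timing of the measures: "Outcome measures objective and subjective will be collected at the beginning and end of the study". MSWS-12 and MSIS-29 are the two patient-completed questionnaires in its list.

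The SAP's table of measures taken at two timepoints covers EDSS, MSIS-29 and MSWS-12. It names the test, "Means from pre to post were compared using a paired samples t-test", and the summary statistics, "Means \pm standard deviations are reported". The two rows at issue are:

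- "MSIS29 | 97.3 \pm 25.2 | -- | 85.0 \pm 20.2 | 0.397"
- "MSWS12 | 0.89 \pm 0.14 | -- | 0.70 \pm 0.28 | 0.277"

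The text above the table states that the p-values are not significant. No number of pairs, degrees of freedom or missing-data statement accompanies these rows. The protocol (Withdrawal of Subjects) left the use of partial data to a later decision with the statistician, and the SAP records no such decision.

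**The concern.** A paired t-test uses only patients with both readings. The only sample size that the SAP states is 7, so a reader takes the two rows as null results in 7 patients. If fewer pairs were tested, the result applies only to patients who completed the questionnaire twice, and the non-significance partly reflects that smaller number. If 7 pairs were tested, at least one figure in the MSWS-12 row is almost certainly wrong. In both cases the table misreports a patient-reported outcome.

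**Working it through.** **Inputs** (SAP, two-timepoint table)

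- MSWS-12: 0.89 (SD 0.14) to 0.70 (SD 0.28), fall 0.19, p=0.277.
- MSIS-29: 97.3 (SD 25.2) to 85.0 (SD 20.2), fall 97.3 - 85.0 = 12.3, p=0.397.
- n = 7, from the SAP's goal.
- Two-sided p is assumed. The SAP does not state sidedness; it says only "SPSS version 28.0 was used for analyses".
- The printed means and SDs are assumed to come from the pairs tested. This is the key assumption and is taken up under the objection.

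**Formulas**

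- t = the t quantile at 1 - p/2 with n - 1 df
- SD of change = fall × √n / t
- r = (SD1² + SD2² - SDchange²) / (2 × SD1 × SD2)

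**MSWS-12, 7 pairs**

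1. p=0.277 with 6 df gives t = 1.1955.
2. SD of change = 0.19 × 2.6458 / 1.1955 = 0.4205.
3. r = (0.0196 + 0.0784 - 0.1768) / 0.0784 = -1.005.

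The SD of a difference cannot exceed the sum of the two SDs, here 0.14 + 0.28 = 0.42. At that limit (r = -1), t = 0.19 × 2.6458 / 0.42 = 1.197 and p = 0.2765. As printed, 0.277 is therefore just out of reach. Taking every rounding margin in the favourable direction (means 0.885 and 0.705, SDs 0.145 and 0.285, p=0.2765) gives r = -0.68. That is the least extreme value possible.

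**MSIS-29, 7 pairs**

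1. p=0.397 with 6 df gives t = 0.9119.
2. SD of change = 12.3 × 2.6458 / 0.9119 = 35.69.
3. r = (635.04 + 408.04 - 1273.7) / 1018.08 = -0.23. The rounding range is -0.26 to -0.20.

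**How unusual these correlations are.** Simulated samples of 7 from a bivariate normal distribution, with assumed true correlations:

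| True correlation (assumed) | Chance of r at or below -0.68 (MSWS-12) | Chance of r at or below -0.20 (MSIS-29) |
|---|---|---|
| 0 | 4.7% | 33% |
| 0.3 | 1.2% | 13% |
| 0.5 | 0.3% | 5% |
| 0.7 | 0.06% | 1% |

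**What 7 pairs would normally give.** From the printed means and SDs:

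| Correlation (assumed) | MSWS-12 p | MSIS-29 p |
|---|---|---|
| 0 | 0.159 | 0.353 |
| 0.5 | 0.084 | 0.209 |
| 0.7 | 0.052 | 0.124 |
| Printed | 0.277 | 0.397 |

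**Other explanations tried at n = 7**

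- One-sided p-values: the implied r is below -5 for both measures, which is impossible.
- An unpaired t-test (12 df): p = 0.134 for MSWS-12 and 0.334 for MSIS-29, so neither printed p is reproduced.
- The ± figures read as standard errors: multiplying by √7 gives SDs of 0.37 and 0.74 for MSWS-12, and 66.7 for MSIS-29 at baseline. These exceed the largest possible SDs (0.34, 0.49 and 61.7) if MSWS-12 is a fraction from 0 to 1 and MSIS-29 a total from 29 to 145. Both ranges are assumptions.

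**The case against.** The strongest reply is that evaluating 7 patients does not promise 7 pairs in every test. The SAP shows smaller denominators elsewhere. The lumbar extension row, "MMT lumbar ext B | 1 | 0 | 4 | 20.0% | 0.0% | 80.0"%, sums to 5, and the rectus abdominis and both biceps femoris rows sum to 6. The two questionnaire rows support no positive claim, and the SAP already calls 7 a very low sample size and asks for caution. This stands in part: unequal numbers are to be expected here. But the categorical table lets a reader count its patients and these two rows do not. The caution concerns a sample of 7 and does not disclose a smaller one.

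A second reply is that a negative correlation is possible in a small, heterogeneous group. For MSIS-29 this stands: -0.23 is unlikely but does not rule out 7 pairs. For MSWS-12 it does not rescue the row, because a correlation of -0.68 or lower would mean that the questionnaire largely reversed the patients' order over six weeks of treatment.

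A reader might go further and infer that only 3 or 4 pairs were tested, so that about half the group was dropped. The back-calculation gives a positive correlation on both rows only at those numbers: 0.62 (MSWS-12) and 0.63 (MSIS-29) with 3 pairs, 0.20 and 0.41 with 4. The documents do not support this, for two reasons.

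- It excludes 5 pairs by assumption. MSWS-12 with 5 pairs implies r between -0.44 and 0.00, which is quite possible.
- It requires the printed means and SDs to come from exactly the pairs tested, which the SAP does not say. Take constructed MSIS-29 totals of 105, 100, 63, 97, 67, 134 and 115 before treatment, and 97, 69, 53, 86, 103 and 102 after it for the first six patients. The means and SDs over all available scores are 97.3 (25.2) and 85.0 (20.2). The test on the 6 pairs gives p=0.397 with r=0.46. Every printed figure is matched with one questionnaire missing.

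**Conclusion.** The point holds for MSWS-12. Its printed row does not fit the only sample size that the SAP states, because 7 complete pairs need a correlation of about -1, and -0.68 at best after rounding. MSIS-29 adds some doubt (r about -0.23) but does not contradict 7 pairs by itself.

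There are two explanations, and the documents cannot separate them: fewer than 7 pairs were tested, or a mean, SD or p-value is wrong. In the second case the error may matter. With 7 pairs and an assumed correlation of 0.5, the MSWS-12 means and SDs would give p=0.084 against the printed 0.277.

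The conclusion rests on a two-sided test and on repeated scores in the same patient not being strongly negatively correlated. If the means and SDs come from a different set of patients than the test, then the test did not use 7 complete pairs, which is the first explanation. The number of pairs cannot be recovered from the table. Nor do the documents show that the reported mean improvements overstate the change in all 7, because nothing is known about any patient who may be missing.

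**What to change.** 1. Re-run the MSIS-29 and MSWS-12 rows from the source data. Compute the means, SDs, mean change with 95% CI, and p on the same set of pairs.
2. Print the number of pairs and the degrees of freedom in each row.
3. If there are fewer than 7 pairs, label the row as a result in patients with both questionnaires and give the number out of 7. Do not present non-significance as the finding for all 7 patients.
4. If 7 pairs do exist, find and correct the wrong figure.

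The cost is a short re-run on data already held and a revised table, with no new visits. A comparison of included and missing patients, or a bound for the missing ones, is optional. The rows may look less precise once the true number of pairs is shown.

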The primary study endpoint of this pilot study to assess if decrease in spasticity for individuals with MS is possible during NeuBie direct current treatment and for any length of time after treatment to further learn if this correlates to improvement in functional gait and transfers. The listed subjective and objective data points are selected to capture this endpoint.

Procedures Involved

Study methods:

1. Treatment portion of study:
2. The physical therapist will implement manual activation techniques combined with NeuBie and PT exercise interventions 3 times per week for 6 weeks.
 - i) Use of Treatment table with manual activations to underactive, spastic or limited in sensory muscles/regions (The PT will consider primary and secondary activations to strengthen neural pathways maximally)
 - ii) NeuBie Mapping mode scanning process with electrode placed on thoracolumbar space and second sponge electrode scanning for:
 - (1) Spots that stimulate movement they couldn't do before per initial assessment
 - (2) Spots that allow movement which is a greater range than available before per initial assessment
 - (3) Spots that lead to decreased spasticity (turn up amplitude and have participant work through the threat response then repeat)
 - (4) Diminished sensation areas – drive signal to increase sensory nerves and become metabolically active. Consider knee, hip and ankle joints as these are neurologically rich.
 - iii) Train using physical therapy exercises with Neubie in training mode and Hz current adjusted for tolerance, ability to work through or decrease spasticity in (500 Hz) in the following areas (spasticity, contraction, dead or diminished spots and hot spots) as tolerated but remove if participant is displaying signs of fatigue
 - (1) Spasticity areas – 500Hz – adjust amplitude to 7/10 discomfort and Pt works through spasticity with assist from PT as needed. The muscle that oppose the spasticity (agonist) will be considered for 40Hz current adjusted no higher than 7/10 discomfort with movement patterns out of the spasticity.
 - (2) Contraction areas -500Hz – adjust amplitude to 7/10 intensity and participant works with contracting muscle without altered kinematics or co-contraction. The muscle that oppose the spasticity (agonist) will be considered for 40Hz current adjusted no higher than 7/10 discomfort with movement patterns out of the spasticity.

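### The protocol asks whether lower spasticity goes with better gait and transfers, but the SAP never relates the two and reports spasticity only as direction-of-change counts

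*SAP*

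**What the plan says.** **Protocol, Study Endpoints.** The primary endpoint is first to "assess if decrease in spasticity for individuals with MS is possible during NeuBie direct current treatment". The same sentence then extends the question to the period afterwards and to function: "for any length of time after treatment to further learn if this correlates to improvement in functional gait and transfers". It has three parts: spasticity during treatment, spasticity afterwards, and the link to function.

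**Protocol, Data Analysis Plan.** Reporting is to be descriptive, with counts and percentages. The section adds that mean, median and mode will be examined, and that the statistician's analysis will refer to minimal clinically significant change on the measures. It names no correlation, composite score or per-person score.

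**SAP, Analyses.** Measures taken at three time points get repeated-measures ANOVA trends, and those taken at two get paired t-tests. For the rest, "The MAT and MMT measures were analyzed descriptively (no p-values"). Each analysis takes one variable at a time.

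**SAP, tables.** MAT appears in 12 movement-by-side rows where "categorical measures are shown by the count and percentage of patients who improved, stayed the same, and worsened over time", from pre to post. The two strongest rows are "MAT R Ankle PF change | 1 | 1 | 5" and "MATL ankle PF change | 2 | 0 | 5" (worse, same, improved). The timed functional measures appear only as group means with standard errors: "TUG Test | 27.2 (9.2) | 23.6 (6.9) | 16.5 (0.4) | 0.321" and "25 foot walk test | 21.4 (5.2) | 20.7 (5.9) | 15.0 (1.3) | 0.370". MSWS-12 is given as pre and post means with standard deviations.

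The SAP does not define MAT. It is taken here to be the Modified Ashworth test in the protocol's outcome list; manual muscle testing is reported separately as MMT.

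**The concern.** The endpoint asks a within-person question: did the people whose spasticity fell also walk and transfer better? Separate one-variable summaries cannot answer it, and nothing in the SAP pairs MAT with TUG, the 25-foot walk or MSWS-12.

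The MAT display also discards three things needed even for the spasticity part:

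- **Starting grade.** The Inclusion criteria require Modified Ashworth 1 to 4 but name no movement. A *same* entry can therefore mean no spasticity at either visit, or spasticity that did not change.
- **Size of change.** Without grades, change cannot be read against any threshold for a meaningful difference, nor can a mean, median or mode of the grades be given.
- **The link between rows.** The reader cannot see how far improvement is concentrated in some participants.

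At stake is an answer, however rough, to a question the pilot was set up to ask.

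**Working it through.** **1. Reproduce the SAP's figures.** The inputs are the 12 MAT rows in SAP order (hip flexion R, L; hip extension R, L; knee flexion R, L; knee extension R, L; ankle DF R, L; ankle PF R, L).

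- Worse: 0+0+1+2+1+0+1+0+1+0+1+2 = 9
- Same: 5+6+2+4+4+3+5+3+6+7+1+0 = 46
- Improved: 2+1+4+1+2+4+1+4+0+0+5+5 = 29
- Total: 9+46+29 = 84 = 12 × 7

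Every row sums to 7 and all 36 percentages reproduce (for example left ankle PF: 2/7 = 28.6%, 5/7 = 71.4%). The 84 entries are clustered in 7 people, so these sums are a check and not an estimate.

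**2. What the rows do establish.** At ankle PF, 5 of 7 improved on each side.

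- Improved on both sides: at least 5+5-7 = 3, at most 5.
- Improved on at least one side: 10 minus the number improved on both, so 5 to 7.

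At least 5 of 7 participants therefore improved somewhere.

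**3. What the rows leave open: concentration.** For each participant, let net = rows improved minus rows worse. The nets sum to 29-9 = 20, a mean of 20/7 = 2.9.

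- Lower bound on participants with net above 0. In any row, two people can hold at most min(improved, 2) of the improvements. Over the rows this is 2+1+2+1+2+2+1+2+0+0+2+2 = 17. The other five then have a combined net of at least 20-17 = 3, so at least one of them is also positive. Two is therefore impossible.
- An integer programme on the row margins (one status per participant per row) gives a range of 3 to 7 of 7.
- The same programme lets the median participant's net be as low as 0 (nets 0, 0, 0, 0, 6, 7, 7) or as high as 6 (nets -2, -1, -1, 6, 6, 6, 6). Both sets sum to 20. They are feasible extremes, not likely values.

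**4. What the rows leave open: size.** Grade steps are not given. If every change were one step, the mean change per entry would be (-29+9)/84 = -0.24. If changes could be one or two steps (an assumption), the limits are (-29+18)/84 = -0.13 and (-58+9)/84 = -0.58.

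**5. Precision if an association is shown.** The interval is tanh(atanh(r) ± 1.96/√(n-3)). For an observed r = 0.5, atanh(0.5) = 0.549.

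| Pairs | 1.96/√(n-3) | Approximate 95% interval |
|---|---|---|
| 7 | 0.98 | -0.41 to 0.91 |
| 6 | 1.13 | -0.52 to 0.93 |
| 5 | 1.39 | -0.68 to 0.96 |
| 4 | 1.96 | -0.89 to 0.99 |

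The range of n is an assumption, because the SAP states no n for TUG or the 25-foot walk. Fewer than 7 is plausible: four MMT rows fall short (rectus abdominis 0+3+3 = 6; lumbar extension 1+0+4 = 5; biceps femoris right 0+2+4 = 6 and left 0+1+5 = 6).

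**The case against.** The best defence is that the SAP did roughly what the Data Analysis Plan described. That section promises counts and percentages and names no correlation. The endpoint wording is loose, asking only whether a decrease is possible and then to learn about a link. The SAP draws no conclusion on spasticity, warns that 7 patients is a very low number and urges caution. A plot of at most seven points will not settle the matter.

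Much of this stands. The missing correlation is a gap against Study Endpoints and not a departure from the Data Analysis Plan. The particular summary and plots proposed below are one reasonable design, not something the protocol prescribes. The caution about sample size, however, concerns precision and does not replace an analysis that was left out. Nor is the Data Analysis Plan fully met for MAT. Direction counts yield a typical direction per row, but no mean, median or mode of the grades and nothing to set against a minimal clinically significant change.

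A reader might go further and infer that the improvement could be confined to a few people. The documents do not support that, since at least 5 of 7 improved on at least one side at ankle PF. What remains open is how concentrated the improvement is. Nor do the tables show that spasticity failed to fall, or that it is unrelated to function. They are silent on the second question.

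**Conclusion.** The point holds as a reporting gap. The SAP gives no answer to the correlation part of the stated primary endpoint, and its MAT table cannot supply one. That table is compatible with anything from 3 to 7 of 7 participants having more rows better than worse, and it hides starting grade and size of change.

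This rests on reading MAT as Modified Ashworth and on taking the endpoint's reference to correlation as a within-person association, which is the natural reading. It does not depend on the assumed grade steps or paired n, which only illustrate size and precision.

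No stated conclusion is reversed, and any association will be very imprecise. The change is minor but worthwhile, because the data are already held and individual results suit a study that the protocol describes as a series of cases.

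**What to change.** Add to the SAP, labelled post hoc and descriptive:

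1. A listing by study number of pre and post MAT grade for all 12 tests, with one summary change per participant. State one numeric coding of grade 1+ and repeat the summary under an alternative coding. Give the group median and the observed range, without a confidence claim.
2. Plots of each participant's MAT change against change in TUG, 25-foot walk and MSWS-12, with the paired n stated for each. Any rank correlation is shown as description only.
3. The existing 12-row table, kept as supporting detail.
4. A statement that neither document gives a minimally important MAT change, that the part of the endpoint about spasticity during treatment is not answered by pre-to-post data, and that Hoffman's reflex, listed as an outcome in the protocol, is not reported in the SAP.

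The cost is some SAP wording, one listing, one summary and three plots, with no new data collection. The downsides should be stated: averaging ordinal grades weights all movements equally, movements graded 0 at both visits dilute the summary, and the choices are made after results are known.
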